APPENDIX D: PPAQ & PPUQ Questionnaire

The PPAQ (Product Performance and Attributes Questionnaire) and PPUQ (Post-Product Use Questionnaire) are included below :

PPAQ1: The PPAQ1 Questionnaire is given to the patient 5 (+ 5) minutes after the product is administered. The patient must answer questions 1-3 below while in clinic.

No.	Question item	Answer
1	Relieving the discomfort of dry mouth	Poor (1) Fair (2) Good (3) Very Good (4) Excellent (5)
2	Effectively moistens your mouth	Poor (1) Fair (2) Good (3) Very Good (4) Excellent (5)
3	Effectively lubricates your mouth	Poor (1) Fair (2) Good (3) Very Good (4) Excellent (5)

PPAQ2: The PPAQ2 Questionnaire is given to the patient 30 (\pm 10) minutes after the product is administered. The patient must answer questions 1-11 below while in clinic.

No.	Question item	Answer
1	Relieving the discomfort of dry mouth	Poor (1) Fair (2) Good (3) Very Good (4) Excellent (5)
2	Effectively moistens your mouth	Poor (1) Fair (2) Good (3) Very Good (4) Excellent (5)
3	Effectively lubricates your mouth	Poor (1) Fair (2) Good (3) Very Good (4) Excellent (5)
4	Feeling comfortable in the mouth	Poor (1) Fair (2) Good (3)

		Very Good (4) Excellent (5)
5	Soothing your mouth	Poor (1) Fair (2) Good (3) Very Good (4) Excellent (5)
6	Allowing you to speak without difficulty	Poor (1) Fair (2) Good (3) Very Good (4) Excellent (5)
7	Helping to freshen your breath	Poor (1) Fair (2) Good (3) Very Good (4) Excellent (5)
8	Protecting your mouth from drying out	Poor (1) Fair (2) Good (3) Very Good (4) Excellent (5)
9	Providing whole mouth comfort	Poor (1) Fair (2) Good (3) Very Good (4) Excellent (5)
10	Helping you to swallow without difficult	Poor (1) Fair (2) Good (3) Very Good (4) Excellent (5)
11	Helping mouth feel 'normal'	Poor (1) Fair (2) Good (3) Very Good (4) Excellent (5)

PPAQ3: The PPAQ3 Questionnaire is given to the patient at three (3) different timepoints (60,120 and 240 minutes).

The first one is given 60 (\pm 10) minutes after the product is administered and must be completed in clinic. The second one is given to the patient 120 (\pm 10) minutes after the product is administered and must be completed in clinic. The third one is given to the patient 240 (\pm 10) minutes after the product is administered and must be completed in clinic or at home. For PPAQ3, the patient must answer questions 12-14 below at each timepoint.

No.	Question item	Answer
12	Having a long-lasting dry mouth relief	Poor (1)

		Fair (2) Good (3) Very Good (4) Excellent (5)
13	Having a long-lasting lubricating effect	Poor (1) Fair (2) Good (3) Very Good (4) Excellent (5)
14	Having a long-lasting moisturizing effect	Poor (1) Fair (2) Good (3) Very Good (4) Excellent (5)

PPAQ4: The PPAQ4 Questionnaire is only given to the patient at Visits 3, 4, 6 and 7. The patient must answer questions 15-23 prior to using any study product because it is a pre-use measurement. This questionnaire must be completed while the patient is in clinic.

No.	Question item	Answer
15	Providing relief all night	Poor (1) Fair (2) Good (3) Very Good (4) Excellent (5)
16	Reducing the number of times you wake up from dry mouth	Poor (1) Fair (2) Good (3) Very Good (4) Excellent (5)
17	Feeling less parched when you wake up	Poor (1) Fair (2) Good (3) Very Good (4) Excellent (5)
18	Having a long-lasting dry mouth relief	Poor (1) Fair (2) Good (3) Very Good (4) Excellent (5)
19	Having a long-lasting lubricating effect	Poor (1) Fair (2) Good (3) Very Good (4) Excellent (5)
20	Having a long-lasting moisturizing effect	Poor (1) Fair (2)

		Good (3) Very Good (4) Excellent (5)
21	Having an overall dry mouth relief	Poor (1) Fair (2) Good (3) Very Good (4) Excellent (5)
22	Having an overall lubrication effect	Poor (1) Fair (2) Good (3) Very Good (4) Excellent (5)
23	Having an overall moisturizing effect	Poor (1) Fair (2) Good (3) Very Good (4) Excellent (5)

PPUQ: The PPUQ Questionnaire is given to the patient only at Visits 4 and 7, 240 (\pm 10) minutes after the product is administered. The patient must answer question 24 below while in clinic.

No.	Question item	Answer
24	Would you continue use of the product?	Yes No

APPENDIX E: The Challacombe Scale

The Challacombe Scale will be provided in a separate document. The Principal Investigator or designee will complete the Challacombe Scale. Per (S Osailan et al, 2011), the Challacombe Scale was developed from research conducted at King's College London Dental Institute under the supervision of [name]. The purpose of this scale is to be able to visually identify and quantify whether your patient has xerostomia (dry mouth) and if so, how it changes over time and the most appropriate therapy options. This scale is applicable whatever your profession. The Challacombe Scale works as an additive score of 1 to 10 : 1 being the least and 10 being the most severe. Each feature scores 1 and symptoms will not necessarily progress in the order shown, but summated scores indicate likely patient needs. Score changes over time can be used to monitor symptom progression or regression.

The Challacombe Scale Score may include the following assessments:

1. Mirror sticks to buccal mucosa2. Mirrors sticks to tongue3. Saliva frothy	An additive score of 1 - 3 indicates mild dryness. May not need treatment or management. Sugar-free chewing gum for 15 mins, twice daily and attention to hydration is needed. Many drugs will cause mild dryness. Routine checkup monitoring required.

4. No saliva pooling in floor of mouth5. Tongue shows generalized shortened papillae (mild depapillation)6. Altered gingival architecture (i.e. smooth)	An additive score of 4 - 6 indicates moderate dryness. Sugar-free chewing gum or simple sialogogues may be required. Needs to be investigated further if reasons for dryness are not clear. Saliva substitutes and topical fluoride may be helpful. Monitor at regular intervals especially for early decay and symptom change.

7. Glassy appearance of oral mucosa, especially palate8. Tongue lobulated/fissured9. Cervical caries (more than two teeth)10. Debris on palate or sticking to teeth	An additive score of 7 - 10 indicates severe dryness. Saliva substitutes and topical fluoride usually needed. Cause of hyposalivation needs to be ascertained and Sjögren's Syndrome excluded. Refer for investigation and diagnosis. Patients then need to be monitored for changing symptoms and signs, with possible further specialist input if worsening.

Statistical Analysis Plan		Page 1 of 17
Sponsor SunBio Inc.	Study Clinical Evaluation of MucoPEG for Xerostomia	Version 1.1

SunBio Inc.

Clinical Evaluation of MucoPEG for Xerostomia

Protocol Number: SB-MU-001
Version 1.1 (8th November 2021)

Statistical Analysis Plan

Version 1.1, 22nd May 2023

Statistical Analysis Plan		Page 2 of 17
Sponsor SunBio Inc.	Study Clinical Evaluation of MucoPEG for Xerostomia	Version 1.1

Version History

Version	Version Date	Author/Title	Summary of Key Changes
1.0	15 Feb 2023	[REDACTED] [REDACTED].	Initial Release.

Statistical Analysis Plan		Page 3 of 17
Sponsor	Study	Version
SunBio Inc.	Clinical Evaluation of MucoPEG for Xerostomia	1.1

1.1	22 May 2023		
1. Change to hypotheses.
 
We discovered after locking of the database that the hypotheses for the primary endpoint were stated incorrectly in the study protocol version 1.1 because the Visual Analogue Scale was constructed such that 0 = no symptom and 10 = most severe symptom. The original hypotheses were:
 
Null hypothesis: Change in VAS after MucoPEG™ minus change in VAS after Biotène® Dry Mouth Gentle Oral Rinse ≤ 0
 
Alternative hypothesis: Change in VAS after MucoPEG™ minus change in VAS after Biotène® Dry Mouth Gentle Oral Rinse > 0
 
Since an improvement in symptom was represented by a negative change in its measurement. The hypotheses in this document have been amended to reflect this finding. The corrected version is:
 
Null hypothesis: Change in VAS after MucoPEG minus change in VAS after Biotène ≥ 0
 
Alternative hypothesis: Change in VAS after MucoPEG minus change in VAS after Biotène < 0
 
2. Modification to the way change in VAS is assessed as a secondary endpoint.
 
In section 7.3 of the protocol, it is stated that: "The secondary endpoints include examination of the temporal changes in the effect of MucoPEG relative to Biotene, measured using the Visual Analogue Scale, after using the products for two

-----	-------------	--	--

Statistical Analysis Plan		Page 4 of 17
Sponsor SunBio Inc.	Study Clinical Evaluation of MucoPEG for Xerostomia	Version 1.1

Version	Version Date	Author/Title	Summary of Key Changes
			hours (at Visit 2 and Visit 5) and one week (at Visit 3 and Visit 6)." This text is ambiguous on the choice of initial value from which the relevant changes are to be measured. Results produced by calculating changes between two successive time points were examined by the Sponsor. The Sponsor requested that changes to be calculated from the baseline value, before any of the products were used after their examination.

Statistical Analysis Plan		Page 5 of 17
Sponsor SunBio Inc.	Study Clinical Evaluation of MucoPEG for Xerostomia	Version 1.1

Document Approval

Author	
Authored By	
Signature	
Date	
Role	Senior Statistician

Approval	
Approved By	
Signature	
Date	
Role	

Approval	
Approved By	
Signature	
Date	
Role	

Approval	
Approved By	
Signature	
Date	
Role	

Approval	
Approved By	
Signature	
Date	
Role	

Statistical Analysis Plan		Page 6 of 17
Sponsor	Study	Version
SunBio Inc.	Clinical Evaluation of MucoPEG for Xerostomia	1.1

Table of Contents

1	Introduction	8
1	Abbreviations	8
2	Study Objectives.....	8
2.1	Primary Objective	8
2.2	Secondary Objective	9
2.3	Primary Endpoints.....	9
2.4	Secondary Endpoints.....	9
3	Study Design.....	10
3.1	Randomization.....	10
3.2	Blinding.....	11
3.3	Study Assessments.....	11
4	Sample Size Determination.....	11
5	Statistical Analyses	12
5.1	General Considerations.....	12
5.1.1	Descriptive Statistics.....	12
5.1.2	Study Day.....	12
5.1.3	Visit Windows	13
5.1.4	Statistical Significance.....	13
5.1.5	Precision	13
5.2	Analysis Populations	13
5.3	Handling of Missing Data	14
5.4	Subject Disposition	14
5.5	Demographics and Baseline Characteristics	14
5.6	Analysis of Study Endpoints	14
5.6.1	Primary Analysis	14
5.6.2	Sensitivity Analysis	16
5.6.3	Secondary Endpoints	16
5.7	Poolability Analysis	16
5.8	Safety Analyses	16

Statistical Analysis Plan		Page 7 of 17
Sponsor SunBio Inc.	Study Clinical Evaluation of MucoPEG for Xerostomia	Version 1.1

5.9	Subgroup Analyses	17
5.10	Interim Analyses	17
5.11	Protocol Deviations.....	17
6	Changes from Planned Analyses	17
7	Subject Listings	17

Statistical Analysis Plan		Page 8 of 17
Sponsor SunBio Inc.	Study Clinical Evaluation of MucoPEG for Xerostomia	Version 1.1

1 Introduction

This statistical analysis plan describes the planned statistical methods to be used during the reporting and analysis of data collected under the Clinical Investigation Protocol “Clinical Evaluation of MucoPEG for Xerostomia”. This statistical analysis plan should be read in conjunction with the study clinical investigation plan and case report forms (CRFs). This version of the SAP has been developed with respect to the Clinical Investigation Protocol “Clinical Evaluation of MucoPEG for Xerostomia”, Version 1.1 (8th November 2021). Any revisions to the protocol or CRFs that impact the planned analyses may require updates to the statistical analysis plan.

Applicable Documents:

Document Number, Version	Document Title
SB-MU-001 Version 1.1	Clinical Evaluation of MucoPEG for Xerostomia (CEMPEG)

1 Abbreviations

Abbreviation/Term	Definition
AE	Adverse events
CRF	Case report form
DMI	Dry Mouth Inventory
DMRQ	Dry Mouth Relief Questionnaires
PPAQ	Product Performance and Attributes Questionnaire
PPUQ	Post-Product Use Questionnaire
SAE	Serious adverse events
VAS	Visual Analogue Scale

2 Study Objectives

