15.3 Statistical Methods

Data will be summarised descriptively as tables and/or graphs. Continuous variables such as patient’s assessment of mouth dryness using the Visual Analogue Scale (VAS) are to be summarised as mean, standard deviation, number of non-missing observations, median, minimum and maximum by the product used (MucoPEG™ or Biotène® Dry Mouth Gentle Oral Rinse) and period (1 – before washout or 2 – after washout). Discrete variables such as ordinal

responses or binary responses (yes or no) from the Dry Mouth Relief Questionnaire, the Product Performance and Attributes Questionnaire, etc. are to be summarised as frequency counts and percentages by product and period.

Measurements of symptom severity will be tested in a Student's t test for the difference between MucoPEG™ and Biotène® Dry Mouth Gentle Oral Rinse in their mean changes in Visual Analogue Scale for each treatment period. Changes between Visit 2 and Visit 4 and between Visit 5 and 7 will be tested for the primary endpoint and changes between Visit 2 and Visit 3, between Visit 5 and Visit 6, within Visit 2 (before the first dose and two hours after the first dose) and Visit 5 (before the first dose and two hours after the first dose) will be tested for the secondary endpoint. Confidence intervals will be presented with significance probability of the difference between the mean values.

Data on other secondary endpoints will be summarised descriptively.

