2.4 Secondary Endpoints

- The difference between MucoPEG and Biotène Dry Mouth Gentle Oral Rinse in the change in rating of mouth dryness.

Mouth dryness will be measured using the Visual Analogue Scale:

- VAS (before), which is measured before using any of the products on the first day of each treatment period, at Visit 2 or Visit 5

Statistical Analysis Plan		Page 10 of 17
Sponsor	Study	Version
SunBio Inc.	Clinical Evaluation of MucoPEG for Xerostomia	1.1

- VAS (after), which is measured two hours after using any of the products on the first day of each treatment period, at Visit 2 or Visit 5
- VAS (1 week), which is measured after the last dose of a product at one week in each treatment period, at Visit 3 or Visit 6

Change in the rating of mouth dryness is the difference from before the products were used, that is, VAS (after) – VAS (before) and VAS (1 week) – VAS (before).

- Assessment of mouth dryness using the Product Performance and Attributes Questionnaire (PPAQ):
 - PPAQ1, PPAQ2 and PPAQ3 at Visit 2, 3 and 4 in Period 1 and at Visit 5, 6 and 7 in Period 2. Patients are to be assessed using PPAQ1 once at 5-10 minutes after administration of the product in each visit, PPAQ2 once at 30±10 minutes, and PPAQ3 three times at 60±10 minutes, 120±10 minutes and 240±10 minutes at each visit.
 - PPAQ4 at Visit 3, 4 in Period 1 and Visit 6, 7 in Period 2.
- Assessment of mouth dryness using the Post-Product Use Questionnaire (PPUQ) at Visit 4 in Period 1 and at Visit 7 in Period 2.
- Assessment of mouth dryness using the Dry Mouth Inventory (DMI) at Visit 2, 3 and 4 in Period 1 and at Visit 5, 6 and 7 in Period 2.

3 Study Design

This study is a randomized, open-labelled crossover trial. Each patient will receive both MucoPEG and Biotène Dry Mouth Gentle Oral Rinse. This study will take place in up to two study sites.

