5.11 Protocol Deviations

Deviations from the procedures outlined in the protocol will be reported on the CRF. Protocol deviations will be summarized for all deviations and by type with event counts and number of subjects with at least one deviation.

6 Changes from Planned Analyses

Any changes to planned statistical analyses determined necessary prior to performing the analyses will be documented in an amended Statistical Analysis Plan and approved prior to the analysis when possible. Any other deviations or changes from the planned analyses deemed necessary due to violation of critical underlying statistical assumptions, data characteristics, or missing data will be clearly described in the clinical study report with justification and rationale.

7 Subject Listings

Subject listings will be provided for protocol deviations and for patients experiencing any side effects or adverse events.

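### The starting value for the one-week secondary VAS change was fixed after the sponsor had seen results on another definition; both versions should be shown and the choice labelled post hoc.

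*SAP*

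**What the plan says.** Protocol 7.3 lists, as a secondary endpoint, the VAS effect of MucoPEG relative to Biotène after two hours and after one week. Protocol 15.3 gives the contrasts as "changes between Visit 2 and Visit 3, between Visit 5 and Visit 6, within Visit 2" and the same within Visit 5, with a t test, confidence intervals and a significance probability.

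The SAP v1.1 version history (22 May 2023), item 2, says of the protocol 7.3 wording: "This text is ambiguous on the choice of initial value from which the relevant changes are to be measured". It continues: "Results produced by calculating changes between two successive time points were examined by the Sponsor". Then: "The Sponsor requested that changes to be calculated from the baseline value, before any of the products were used after their examination". Item 2 carries no date of its own. Item 1 of the same version begins "We discovered after locking of the database that the hypotheses for the primary endpoint were stated incorrectly".

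SAP 2.4 now states one rule for both time points: "Change in the rating of mouth dryness is the difference from before the products were used". SAP 5.6.3 summarises secondary endpoints descriptively, with confidence intervals for each product by period and combined. Neither section keeps the successive-time-point version, even as a supporting analysis.

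SAP section 6 covers later changes: "Any changes to planned statistical analyses determined necessary prior to performing the analyses will be documented in an amended Statistical Analysis Plan". The sentence goes on to ask for approval before the analysis where that can be done. Other changes, for reasons the section lists, go into the study report with a rationale.

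**The concern.** An open choice of definition does little harm when it is closed before anyone sees results. Here the SAP's own account puts the look first and the choice second. The log explains why some choice was needed. It does not say why this one was preferred once results had been examined.

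What is at stake is how the one-week secondary result can be read. If the two definitions give different pictures, a reader shown only one cannot fully judge how far the conclusion depends on the choice. The note in the version table reveals that another analysis existed but does not show what it found.

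**Working it through.** No planned figure exists on this point. The check compares the texts, then sizes the risk under stated assumptions.

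**1. Did the protocol settle the starting value?** No. Protocol 15.3 names Visit 2 to Visit 3 and Visit 5 to Visit 6. Protocol 9.3 and 9.6 take the VAS twice at Visits 2 and 5, before use and at 120 minutes, so two starting values exist for the one-week change.

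**2. Which endpoint is affected?** The two-hour change runs from before use to two hours under either definition. Only the one-week change moves.

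**3. How do the definitions differ?** Write B for the pre-use reading and H for the two-hour reading at the first visit of a period, and W for the one-week reading. If the successive version was W − H, then

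W − B = (W − H) + (H − B),

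and the baseline version adds the two-hour change to the successive one. This pairing is an assumption. Protocol 9.4 also takes the VAS twice at Visit 3, before use (P) and at 120 minutes (W). The log does not say which pairs were used:

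| Successive version | Baseline version (W − B) minus successive version |
|---|---|
| W − H | H − B |
| P − H | (W − P) + (H − B) |
| W − P | P − B |

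**4. What could selection do to an error rate?** Assumptions: two null contrasts, each judged at one-sided 0.05 (critical value 1.645), jointly normal with correlation ρ, and the more favourable one kept. The chance of a false favourable result is

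P = 1 − Φ₂(1.645, 1.645; ρ),

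where Φ₂ is the bivariate normal distribution function. At ρ = 0 this is 1 − 0.95² = 0.0975.

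| ρ | 0 | 0.3 | 0.5 | 0.7 | 0.9 | 1 |
|---|---|---|---|---|---|---|
| P | 9.75% | 9.3% | 8.8% | 8.0% | 6.8% | 5% |

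The documents give no correlation. As one reference case, suppose the pairing is W − H and that B, H and W have equal variance σ² and equal correlation r. Then cov(W − B, W − H) = σ²(1 − r) and each variance is 2σ²(1 − r). So ρ = 0.5 and P is 8.8%.

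**5. Does the SAP contain such a test?** SAP 5.6.3 does not: it gives summaries and intervals. Protocol 15.3 does. The table in step 4 therefore applies only if that test is run or an interval is read as one.

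**The case against.** There is a good case for leaving this alone, and much of it stands.

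- **The replacement is sound.** It uses the pre-first-dose value, as the primary endpoint does in protocol 7.3, 15.1 and 15.4 and SAP 2.3. It is a natural reading of an objective about effect after one week of use; a change starting two hours after the first dose would miss part of that effect. A switch made for consistency, whatever the results showed, leaves the error at 5%.
- **It is disclosed.** The ambiguity, the prior look and the sponsor's request are all in the same SAP.
- **The endpoint is descriptive.** No between-product test of the one-week change is planned in SAP 5.6.3.
- **The point estimate may be recoverable.** If the pairing was W − H and the same patients contribute, subtracting the reported two-hour mean from the one-week mean gives the omitted value. Its confidence interval cannot be recovered that way, and the pairing is not stated.

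Three stronger readings are tempting and are not supported. A reader might infer that the sponsor picked the definition that suited MucoPEG. The documents give no direction of result and do not say whether the results examined were split by product. A reader might infer that the trial's error rate is inflated, but that needs a test and a result-dependent choice. A reader might infer a breach of SAP section 6, but its approval clause applies only where possible, so it does not bar recording a later change in an amended SAP. Nor does any passage say that the study report will leave out the other results.

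What remains is that a reasonable definition chosen after looking at results is still post hoc, and the plan does not ask for the alternative to be shown.

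**Conclusion.** The point holds as a matter of transparency for one secondary endpoint. The order of events is stated in the SAP, protocol 15.3 had not fixed the starting value, and SAP 2.4 and 5.6.3 carry only the version chosen afterwards.

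As the SAP stands, the effect is on interpretation and no formal error rate is involved. The range of 5% to 9.75% (correlations from 1 to 0) is an illustration. It rests on a test being run or an interval being read as one, on the better of two definitions being kept, and on an unknown correlation.

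Two facts cannot be checked from the documents: the wording of SAP v1.0, and when the sponsor's examination took place. The primary endpoint's starting value is not affected.

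**What to change.** In SAP 2.4 and 5.6.3:

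- report the one-week VAS change, with confidence intervals, under both definitions side by side;
- state which time points the successive version used, including which Visit 3 and Visit 6 reading;
- label the baseline version as chosen after results were seen, and draw no confirmatory claim from it.

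In the study report, describe the change with its rationale, and say who had seen which results, when, and whether by product.

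The cost is one extra table row and a footnote, since the successive results have already been produced. The small downside is that the secondary result is visibly post hoc. If the two versions agree, showing both supports the sponsor's reading.
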